Functional profiling – HUMAnN2. Functional profiling of the microbial community will be done using HUMAnN2 (5). The standard recommended workflow will be followed with modifications to the nucleotide and translated alignment steps. Briefly, nucleotide alignment is performed using bbmap (3) with the bloom filter enabled (bloomk=22) and fast search settings generating a HUMAnN2 compatible SAM file output. The translated alignment step is performed using diamond (6; version 0.9.26). This creates the default pathway abundance and coverage tables, as well as gene family abundance output files per sample. Post-processing of the per-sample tables is done using a combination of HUMAnN2 utility scripts and in-house code designed to clean up the tables for better readability. The three default outputs are each merged across samples using ‘humann2_join_table’ script. Merged pathway abundance and gene families tables are also normalized to relative abundances using ‘humann2_renorm_table’ script. All tables are split into stratified (by Taxa) tables and unstratified (metagenome) tables. Additional tables are generated by regrouping the UniRef90 gene families into other functional categories using the ‘humann2_regroup_table’ script with ‘uniref90 to ko’ and ‘uniref90 to ec’ utility mapping databases. The output tables for KEGG Orthogroups (KOs), molecular functions represented in terms of functional orthologs, and Level-4 enzyme commission (EC), categories of numerical nomenclature that classifies enzymes based on the overall reaction catalyzed, are merged across samples as described above. Using the legacy KEGG databases included with HUMAnN 1.0, gene families outputs are converted to KEGG Pathways (a collection of manually drawn pathway maps representing our knowledge of the molecular interaction, reaction and relation networks) and KEGG Modules (manually defined functional units of gene sets and reaction sets). This is done by processing the gene families default output tables through the ‘humann2’ script specifying the ‘pathways-database’ for the KEGG Pathways and KEGG Modules. The abundance and coverage output tables are merged as described above.

Functional profiling – HUMAnN3. Functional profiling of the microbial community will be done using HUMAnN3 (7). The standard recommended workflow will be followed with modifications to the nucleotide and translated alignment steps. Briefly, nucleotide alignment is performed using bbmap (3) with the bloom filter enabled (bloomk=22) and fast search settings generating a HUMAnN3 compatible SAM file output. The translated alignment step is performed using diamond (6; version 0.9.26). This creates the default pathway abundance and coverage tables, as well as gene family abundance output files per sample. Post-processing of the per-sample tables is done using a combination of HUMAnN3 utility scripts and in-house code designed to clean up the tables for better readability. The three default outputs are each merged across samples using ‘humann_join_table’ script. Merged pathway abundance and gene families tables are also normalized to relative abundances using ‘humann_renorm_table’ script. All tables are split into stratified (by Taxa) tables and unstratified (metagenome) tables. Additional tables are generated by regrouping the UniRef90 gene families into other functional categories using the ‘humann_regroup_table’ script with ‘uniref90 to ko’ and ‘uniref90 to ec’ utility mapping databases. The output tables for KEGG Orthogroups (KOs), molecular functions represented in terms of functional orthologs, and Level-4 enzyme commission (EC), categories of numerical nomenclature that classifies enzymes based on the overall reaction catalyzed, are merged across samples as described above. Using the legacy KEGG databases included with HUMAnN 1.0, gene families outputs are converted to KEGG Pathways (a collection of manually drawn pathway maps representing our knowledge of the molecular interaction, reaction and relation networks) and KEGG Modules (manually defined functional units of gene sets and reaction sets). This is done by processing the gene families default output tables through the ‘humann’ script specifying the ‘pathways-database’ for the KEGG Pathways and KEGG Modules. The abundance and coverage output tables are merged as described above.

References

- 1) Human Microbiome Project, C. (2012). "Structure, function and diversity of the healthy human microbiome." *Nature* 486(7402): 207-214.
- 2) Human Microbiome Project, C. (2012). "A framework for human microbiome research." *Nature* 486(7402): 215-221.

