Synbiotics combine probiotics (alive bacteria) and prebiotics (bacteria food) in order to improve microorganism survival and activity within the host.²³ The synbiotic that will be used in this trial contains the oligosaccharide-degrading probiotics, *A. muciniphila* and *Bifidobacterium infantis*; butyrate producers such as *Clostridium beijerinckii*, *Anaerobutyricum hallii*, and *Clostridium butyricum*; and chicory-derived inulin, a prebiotic dietary fiber. Butyrate is a gut-derived short chain fatty acid suspected to play a role in weight regulation and insulin resistance.²⁴ Butyrate administration in mice models of obesity improves weight and fat mass regulation, increases lipid oxidation in brown adipose and liver tissue, and stimulates the production of gut-derived neuropeptides involved in energy homeostasis and food intake, such as GIP, GLP-1, PYY, and serotonin, and decreases fasting insulin.²⁵⁻²⁷ A previous pilot clinical trial indicated the synbiotic that will be used in the current study to be safe and tolerable as well as effective in reducing HbA1c and improving post-prandial glucose control in individuals with type 2 diabetes mellitus (T2DM) and overweight or obesity,²⁸ however, no studies have analyzed the effect of the synbiotic on body composition, anxiety, and depression in individuals with overweight who do not have T2DM.

References:

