60 participants ages 18-50 that have a BMI between 25.0-40.0 kg/m², who do not also have type 1 or type 2 diabetes mellitus (T1DM or T2DM) will be recruited. Exclusion criteria include: being vegetarian, vegan, carnivore, or keto; pregnancy or planning pregnancy during the study period; lactating women; having a history of inflammatory bowel disease, colon cancer; having been diagnosed with T1DM or T2DM; active cancer; currently participating in a weight loss intervention (dietetic or medication); use of antibiotics, antifungals, or antivirals in the last 3 months; currently taking metformin, GLP-1 agonists, insulin, or fiber supplement; having taken PPI, stimulant laxatives, probiotics, or immunosuppressants in the last month; history of recent (within 30 days) diarrhea illness (including bacterial or viral enteritis or enteric parasitic infection); having a known

hypersensitivity to any component of the study product; having an acute infection or inflammatory condition over the past 4 weeks; having >10% weight variation in the last 6 months; history of bariatric surgery in the past with exemption of laparoscopic band that has been removed.

12) Recruitment Procedure: Describe your recruitment strategies in great detail including how and where the potential participants will be approached and by whom. Will recruitment involve a point of contact on behalf of the study team? Who and how will recruitment material(s) be distributed? Describe precautions that will be taken to minimize the possibility of undue influence or coercion. Include copies of the recruitment emails, flyers, social media post, etc. in your submission as attachments or appendices following the recruitment guidelines.

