In the first visit, participants will come for 45 minutes to the Rickel Department where they will receive a complete explanation of the protocol and will process to sign the "Informed Consent to Participate in Research and Authorization to Collect, Use, and Share their Health Information" if agreeing to participate. Participants' height and weight will be measured to ensure they meet BMI inclusion criteria. Height will be measured using a standard stadiometer and weight will be measured using a standard calibrated digital scale. Their race will be asked to help in data interpretation. Height, weight, race and other information relevant to antibiotic prescription such as date of birth, allergies to medications, and preferred pharmacy will be collected at this time point using our document titled "checklist 2". All symbiotic and placebo bottles will be entirely similar with exemption of individual codes that will vary every 3 bottles. This is because each participant will be provided at the beginning of the study with 3 bottles (with similar code) to ensure enough supply for the 12-week supplement intervention. The company Pendulum will perform an *a priori* randomization of the entire study by using blocked randomization with randomly selected blocked sizes with the intention to reduce bias and ensure balance between groups. This randomization will be added into an Excel document in which they will specify the order of the participant in column 1 (example: Participant 001, Participant 002), the code of the bottles in column 2, and the interpretation of the code (placebo vs probiotic) in column 3. A researcher, independent from this study ([name]), will save in different protected locations (Box, secured laptop, protected USB) the randomization document. [name] will share with [name] an Excel document containing column 1 and column 2 of the provided document (the order of participant and the code of the bottles, without the interpretation of each code). [name] will use the supplement code as the participants' IDs and study data will be added to this Excel document. Both documents, from, [name] and from [name], will be merged at the end of the study, once data has been analyzed to figure out the intervention group to which each participant belonged. During the first

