visit, depending on the order they enrolled, participants will receive the 3 bottles containing the assigned code. Participants will also be provided with two stool sample collection kits, a 3-day diet record form, a 3-day prescription of antibiotics (500 mg of generic Vancomycin every 8h), date for second appointment, and a start date for the antibiotic regimen. The 3-day antibiotic treatment provided prior to beginning the 12-week synbiotic intervention is given with the intention to increase the number of available bacterial niches (bacterial homes/space) and thus increase the engraftment of the newly ingested bacteria. Although participants will be asked to pay the cost of the generic antibiotic treatment initially (which should have an estimated cost of \$20-25), we will offset the cost of the antibiotic by providing the participants with a \$50 Amazon gift card in their second appointment, so they will not be responsible for any costs to participate in this study. This initial gift card is in addition to their \$100 Amazon gift card provided at the end of the study in appreciation for having taken part in this project. Their insurance will not be charged for any study-related testing; however, they are welcome to (but don't have to) use their insurance to buy the antibiotic. During this first visit, participants will have their 1) first 12h fasted blood collection and will be instructed to 2) fill out a 3 day food log before each stool sample collection, 3) collect a stool sample before the start of the antibiotic regimen, 4) collect a stool sample within 12-48 hours after the last dose of the antibiotic regimen, 5) bring both stool samples and diet records with them to the second appointment and, 6) fast 12 hours prior to the second appointment (refrain from the consumption of all food and liquids, except water). The first appointment is expected to take no greater than 45 minutes.

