Participants will receive two cards, a \$50 Amazon gift card after the 2nd appointment and a \$100 Amazon gift card upon completion of the study. Participants will not receive compensation if they withdraw or are unable to complete the study. Additionally, participants will receive free body composition results and interpretation of the BOD POD and DEXA scans at the end of the study. Two BOD PODs and two DEXA scan amount to ~\$400 in monetary market value. Participants will also receive at the end of the study their blood work results (glucose, insulin, HbA1c) and their psychological results (anxiety, depression, and cravings). Results will be disclosed to participants earlier if researchers consider that not disclosing could jeopardize the health and well-being of the individual. Participants with high anxiety and/or depression scores can use one of the following options to obtain psychological support:

- If you are a TCU student you can access to psychological health through several ways: psychiatric evaluations, 24/7 telephone counseling helpline, peer support communities, personalized interventions for student athletes, etc. (<https://counseling.tcu.edu/student-services/#StudentAthletes>)
- If you are not a TCU student, you can find free government support through Texas Health and Human Services by accessing the following link and filling out the form (<https://resources.hhs.texas.gov/pages/find-services>). This form will be used to provide you with the best phone number to contact based on your needs and based on your location. If you prefer to use a phone number you can call [contact] and they will help you to get in touch with a health professional.
- If you live in Tarrant County you can directly call MHMR of Tarrant County (My Health My Resources) at [contact].

18) Procedures to Maintain Confidentiality: Describe how the data will be collected, de-identified, stored, used, and disposed to protect confidentiality. If protected health information is to be re-identified at a later date, describe the procedure for doing so. All signed consents and hard data must be stored for a minimum of 3 years in a locked filing cabinet (and locked room) in the principal investigator's office, lab, or storage closet at TCU. Your professional society may recommend keeping the materials for a longer period of time.

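### Entry requires no prior diabetes diagnosis rather than no diabetes, and no glycaemic check or analysis rule covers undiagnosed cases, which would add noise to the glucose, insulin and HbA1c comparisons and blur the population studied

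*Combined protocol and SAP*

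**What the plan says.** The protocol defines the population in two ways.

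- **No diabetes.** Section 11 (Subject Population) plans for "60 participants ages 18-50 that have a BMI between 25.0-40.0 kg/m²", and adds "who do not also have type 1 or type 2 diabetes mellitus (T1DM or T2DM) will be recruited". Section 9 (Background) says the product was "effective in reducing HbA1c and improving post-prandial glucose control in individuals with type 2 diabetes mellitus", and places the gap in knowledge in people with overweight who do not have that disease.
- **No diagnosis.** Section 8 (Purpose) describes the stage 1 participants as having no diabetes diagnosis. The exclusion list in section 11 uses the same test: "having been diagnosed with T1DM or T2DM". The related drug exclusion, "currently taking metformin, GLP-1 agonists, insulin, or fiber supplement", catches treated disease only.

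Sections 12 and 13 take eligibility from a screening survey reached by QR code. At visit 1 the one eligibility item checked by measurement is BMI: "Participants' height and weight will be measured to ensure they meet BMI inclusion criteria" (section 14). The same visit includes the "first 12h fasted blood collection", with no stated analyte and no stated role in eligibility. Fasting glucose, fasting insulin and HbA1c are described under visit 2, before product is taken, and are repeated at visit 3.

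Section 19 (Data Analyses) plans t-tests within and between groups at p<0.05. It states no adjustment for baseline glycaemia and no rule for participants with diabetic-range values. Section 17 adds: "Results will be disclosed to participants earlier if researchers consider that not disclosing could jeopardize the health".

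**The concern.** A person with unrecognised type 2 diabetes passes every entry check that the protocol describes. That person belongs to the population in which the protocol says the product has already been tested, not to the one in which it says evidence is lacking. Such participants are also likely to have larger and more variable changes in glucose and HbA1c than the rest. With about 30 per arm, a few of them widen the standard error and carry more weight than their number suggests.

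There is a second, less certain route. A participant told early of a high value might start outside treatment during the 12 weeks. The drug exclusions apply at entry, and section 19 does not say how treatment started later is handled.

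At stake are the precision of the metabolic comparisons and whether the report can describe its result as applying to people without diabetes.

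**Working it through.** **What the documents supply.** N = 60 and alpha 0.05. They give no power calculation, SD, effect size or prevalence of undiagnosed diabetes, so there is no planned figure to reproduce.

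**Assumptions.** 1:1 allocation (30 per arm); two-sided test; undiagnosed prevalence p = 1-5%; SD of HbA1c change 0.2 points without diabetes and 0.6-1.0 (central value 0.8) with undiagnosed diabetes.

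**1. Chance of entry.** Expected cases = 60p: 60 × 0.01 = 0.6 and 60 × 0.05 = 3.0. P(at least one) = 1 − (1 − p)^60: 1 − 0.99^60 = 0.45 and 1 − 0.95^60 = 0.95. The chance that the arms differ by two or more cases is 5.5% at p = 1% and 36% at p = 5%.

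**2. Leverage of a single case.** SE of the arm difference = 0.2 × √(2/30) = 0.052. One case falling 1.0 point more than the rest moves an arm mean by 1.0/30 = 0.033, which is 0.65 SE. At 0.5 points it is 0.017, or 0.32 SE. The case also inflates the SD: with one case at 1.0 point the average pooled SD is about 0.237, so the SE is 0.237 × √(2/30) = 0.061 and the shift is 0.033/0.061 = 0.54 SE.

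**3. False positives, simulated t-tests with no treatment effect in the other participants.**

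| Situation | Rejection rate |
|---|---|
| Cases fall at random across arms, p = 1-5%, SD 0.8 in cases | 4.5-4.8% |
| 1 case in one arm, 1.0 point | 4.7% |
| 2 cases, same arm, 1.0 point each | 8.6% |
| 3 cases, same arm, 1.0 point each | 16.6% |
| Only undiagnosed cases respond (0.6 points each), p = 1-5% | 4.4-5.5% |

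**4. Power.** With no cases, 0.145/0.052 = 2.8 SE, and simulated power is about 79%. The mixture SD is √[(1 − p) × 0.2² + p × 0.8²]: at 1%, √(0.0396 + 0.0064) = 0.21; at 5%, √(0.038 + 0.032) = 0.26. Simulated power, with the same 0.145-point effect in everyone:

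| Prevalence | SD in cases 0.6 | 0.8 | 1.0 |
|---|---|---|---|
| 1% | 76% | 74% | 72% |
| 5% | 66% | 59% | 53% |

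**5. Screening cost.** People needed to randomise 60 = 60/(1 − p): 60/0.99 = 60.6, so 61; 60/0.95 = 63.2, so 64. That is 1-4 extra.

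**The case against.** A reader might infer that one or two undiagnosed cases could create or drive a glycaemic result. The arithmetic does not support that. One case moves the difference by well under the roughly 2 SE needed, and its own variance pulls the test back to about its nominal level. Two cases in the same arm reach only about 8-9%. Randomisation keeps the between-arm error near 5% on average. The within-arm pre/post tests in section 19 lack that protection.

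A reader might also infer that the exclusion contradicts the trial's objective. It does not contradict section 8, which asks only for no diagnosis. The documents disagree among themselves, with section 8 and the exclusion on one side and section 9 and the opening of section 11 on the other.

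Three further objections stand in part.

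- Every quantity beyond N and alpha is assumed. The 18-50 age range and recruitment that begins among university staff and students may put prevalence at or below the low end.
- Reliance on self-report is an inference from survey-based screening. The questionnaires and the visit 1 checklist are not shown, so it can only be said that no other check is described.
- The early-disclosure route needs several unquantified events in sequence and carries no weight in the figures above.

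Stage 1 is also exploratory, with several outcome families and none named primary. That limits the consequence but leaves the gap in place.

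**Conclusion.** The concern holds in a limited form. Undiagnosed diabetes can enter through the procedures described, and no eligibility or analysis rule uses the glycaemic values that would reveal it. The expected harm is lost precision, some leverage in the glucose, insulin and HbA1c comparisons, and doubt about whom the result describes. Bias in the between-arm test is not expected.

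Under the stated assumptions the power loss for HbA1c is about 3-7 percentage points at 1% prevalence (79% to 72-76%) and 13-26 at 5% (79% to 53-66%). These figures depend on the assumed prevalence and SDs, and lower prevalence would shrink them. No calculation was made for glucose or insulin. The point deserves correction mainly because the analytic part of the remedy is free.

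**What to change.** 1. **Section 19.** For fasting glucose, insulin and HbA1c, pre-specify a between-arm analysis adjusted for the pre-product (visit 2) value. Add a sensitivity analysis excluding participants whose pre-product glucose or HbA1c is in the diabetic range, by a recognised threshold that the investigators fix before unblinding. Selection on a pre-product value preserves the randomised comparison. The cost is a few lines of text, with no new data.

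2. **Sections 8, 9 and 11.** State whether the population is people without a diagnosis or people without diabetes, and use one wording throughout.

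3. **Section 14.** State what the visit 1 blood is tested for. Reconcile the two accounts of when coded bottles are issued: the first-visit text hands them out at visit 1 by order of enrolment, and the second-visit text supplies them at the end of visit 2.

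4. **If the answer to item 2 is people without diabetes,** use the visit 1 fasted sample for eligibility and read the result before a code is assigned. Reading it only before product starts could exclude people who already hold an allocation. The cost is one assay per participant on blood already drawn, and about 1-4 extra people screened at 1-5% prevalence.

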- 1) **Date:** 12/18/23
- 2) **Study Title:** Supplementation with a Next Generation Synbiotic in Individuals with Overweight or Obesity: A Triple-Blinded Randomized Controlled Trial
- 3) **Principal Investigator (must be a TCU faculty or staff):** [name]
- 4) **College/School:** Texas Christian University
- 5) **Other Investigators:** List all faculty, staff, and students conducting the study. For those not affiliated with TCU, please provide their names and institution.
[name], [name], [name], [name], [name], [name], [name], [name], [name], [name], and [name]
- 6) **If you have internal or external funding for this project –**
Funding Agency: The supplement company Pendulum will provide the product (probiotic and placebo with a market value of \$50,400). The Dean's Opportunity Fund will provide \$49,512 for blood analyses, blood and stool sample tubes, and stool sample whole genome sequencing. [name] will provide part of her start up funds (\$6,000) for participants compensation. **Project #: IRB#2023-345** **Date for Funding:** November 2023
- 7) **If you intend to seek/are seeking internal/external funding for this project –**
Funding Agency: TCU Graduate SERC Grant
Amount Requested From Funding Agency: \$2,000
Due Date for Funding Proposal: October 23rd, 2023
- 8) **Purpose: Describe the objectives and hypotheses of the study and what you expect to learn or demonstrate:** Our proposed triple-blinded, placebo controlled, randomized clinical trial is divided into two stages.
The first stage will consist of exploring the effect of next generation synbiotic supplementation for 12 weeks on body composition, insulin sensitivity, gut microbiota composition and diversity, depression, anxiety, and food cravings in 60 individuals with overweight or obesity who have no diagnosis of diabetes mellitus (DM). For this first stage, we hypothesize that this next generation synbiotic will decrease adiposity, overall body weight, anxiety, depression, and food cravings and increase insulin sensitivity, and gut microbiota diversity. We also hypothesize that the levels of bacterial species in the symbiotic will increase in the gut microbiome.

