Next Generation Probiotics have been created as a result of recent scientific advances.⁸ *A. muciniphila* is one of the next generation species that has independently shown anti-obesity potential.⁹ *A. muciniphila* is inversely correlated with body weight, fat mass, fasting glucose, and hedonic eating.¹⁰⁻¹² *A. muciniphila* is a gram-negative anaerobic bacteria and therefore it is difficult to grow in the lab. Pendulum® (the company that will donate the product to TCU), which possesses a patented strain of *A. muciniphila*, has been able to create an oxygen-free manufacturing process to cultivate and grow this bacterial specie. In mice, its administration has shown to be sufficient to protect from diet induced obesity and insulin resistance.¹³ In humans, *A. muciniphila* supplementation at a concentration of 10^{10} bacteria per day for 12 weeks is safe and effective and can improve metabolic parameters such as body weight, fat mass, and insulin resistance in volunteers with overweight or obesity who are insulin-resistant.¹⁴ In addition to physical benefits, preliminary research indicates *A. muciniphila* to have potential psychological benefits.¹⁵ In mice and humans, depression and anxiety are significantly associated with decreased *A. muciniphila* abundance.¹⁶⁻²² Furthermore, *A. muciniphila* supplementation in mice with chronic restraint stress-induced depression resulted in significantly diminished depression-like behavior.¹⁹ Additionally, FMT from healthy patients decreased anxiety and depression in patients with refractory irritable bowel syndrome or ulcerative colitis, changes that were associated with higher abundance of *A. muciniphila*.^{21,22}

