TCU staff and students will be approached for recruitment via IRB-approved email (colleagues will be asked the favor to send the recruiting email to their current students), posters, flyers, and social media ads in English and Spanish. Posters and flyers will be posted in strategic locations such as dining halls, TCU cafeterias, dorms, bathrooms, gym, etc. as well as electronically on the Nutrition Department's webpage and Pendulum's webpage (supplement company). Ads will also be posted in strategic locations outside TCU such as gyms, cafeterias, health care centers, recreation centers, etc. Social media adds will be published in the professional Instagram page of the PI ([name]) and the professional Instagram and Facebook pages of the Nutrition Department (TCUNutrition and TCU Department of Nutritional Sciences, respectively), as well as through paid adds both in Facebook and Instagram. These recruitment methods will contain a QR code that links to a screening survey to evaluate participant eligibility. Precautions that will be taken to minimize undue influence or coercion: reiterate that participation is voluntary when dispersing recruitment materials, include all required elements aligned with TCU's recruitment guidelines for advertisement materials, and refrain from singling out students and staff that are familiar with or have personal ties to individuals on the research team.

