The triple blinding nature of this study means that participants, researchers (including the PI), and statisticians cannot be made aware of the randomization allocation. Therefore, debriefing to participants can only take part until after data has been analyzed. Once all participants have finalized their interventions and all data has been analyzed, researchers will contact back participants to verbally give them the debriefing statement and inform them which supplement/placebo they received.

14) Study Procedures: Provide a chronological description of the procedures, tests, and interventions that will be implemented during the course of the study. Indicate the number of visits, length of each visit, and the time it would take to undergo the various tests, procedures, and interventions. If blood or tissue is to be collected, indicate exactly how much in volume and all procedures that will be done with collected samples. Describe when, where and how collection will take place. Flow diagrams may be used to clarify complex projects. For Non-TCU study team members please explain their study team role in detail. If the study involved deception justify the use of deception and explain why deception is necessary to achieve the goals of the study. Explain if alternative methods not involving use of deception were considered and why these methods are not being used.

STAGE 1

For stage 1, participants will come to TCU on three days total:

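### Advertising on the manufacturer's webpage with only a one-month probiotic exclusion leaves past users of the trial product eligible; a screening question and an exclusion line would close the gap

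*Combined protocol and SAP*

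**What the plan says.** Section 12 lists email, posters, flyers, off-campus advertisements and social media, "as well as electronically on the Nutrition Department's webpage and Pendulum's webpage (supplement company". Section 9 (Background) identifies this firm as "the company that will donate the product to TCU", and section 6 says that it "will provide the product (probiotic and placebo with a market value of" $50,400.

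In section 11 the only criterion that bears on earlier use of such a product is "having taken PPI, stimulant laxatives, probiotics, or immunosuppressants in the last month". The one criterion that names the study product concerns "hypersensitivity to any component of the study product", not previous use. The same list sets a longer look-back for another exposure that alters the microbiota: "use of antibiotics, antifungals, or antivirals in the last 3 months".

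On blinding, section 13 (Consenting Procedure) states that "participants, researchers (including the PI), and statisticians cannot be made aware of the randomization allocation". Section 14 (Study Procedures) says "All symbiotic and placebo bottles will be entirely similar with exemption of individual codes". No section describes whether the contents match in look, smell or taste, what the placebo consists of, or any check of blinding.

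**The concern.** A person who has taken the product before has a reference that other participants lack. If the capsules or their after-effects differ between arms in a way that can be noticed, that person may work out which arm they are in. Anxiety, depression and cravings are named in the stage 1 hypotheses and are measured by questionnaires that the participant fills in, so they are open to expectation. Randomisation does not remove this effect. Past users who recognise the active product and past users who recognise the placebo would be pushed in opposite directions, so the arms would separate even if past users were split evenly.

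The second route is carry-over. Section 8 (Purpose) expects the product's own species to increase in the gut. If earlier use left those species in place at baseline, the rise still to be seen would be smaller.

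**Working it through.** The plan states no power calculation, effect size or SD, so there is no figure of its own to reproduce. The check has two parts.

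**Eligibility, read from the text.** Take a person who used the trial product and stopped five weeks before screening.
- Probiotic in the last month: not met, so not excluded.
- Hypersensitivity to the product: not met, so not excluded.
- No other listed criterion refers to previous use of the product.

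This person is eligible if the remaining criteria are satisfied. In the analysis, section 19 foresees statistical adjustment only for dietary variables.

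**Possible size of a recognition bias (illustration).**

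From the documents: 60 participants (section 11); two-sample t-tests with p < 0.05 (section 19).

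Assumed: 30 per arm, since the allocation ratio is not stated; a two-sided test; a share f of past users from 0 to 30%; every past user recognises their arm; expectancy moves self-report by 0.3 SD towards benefit in the active arm and 0.3 SD the other way in the placebo arm.

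Bias = 2 × 0.3 × f, in SD units.

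Standard error of the difference in means = √(2/30) = 0.258 SD.

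The last column is the two-sided rejection rate of a t-test with 58 degrees of freedom when the product has no true effect.

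| Share f | Past users of 60 | Bias (SD) | Bias / SE | Type I error |
|---|---|---|---|---|
| 0% | 0 | 0 | 0 | 5.0% |
| 10% | 6 | 0.06 | 0.23 | 5.6% |
| 20% | 12 | 0.12 | 0.46 | 7.4% |
| 30% | 18 | 0.18 | 0.70 | 10.5% |

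A milder case: with f = 5% and half of them recognising their arm, the bias is 2 × 0.3 × 0.05 × 0.5 = 0.015 SD, which is negligible.

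**Carry-over.** If a share f of participants lose a fraction c of the rise they would otherwise show, the mean rise is multiplied by (1 − f × c). For f = 10% and c = 50% this is 0.95. For the extreme f = 30% and c = 100% it is 0.70. Both f and c are assumptions; the documents give neither.

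**The case against.** The strongest reply is that the problem may hardly arise. The webpage is one of many channels, all three visits are in person on one campus, and the participants are aged 18-50 with a BMI of 25-40 and no diabetes. The earlier trial of this synbiotic that the protocol cites was in people with type 2 diabetes, who are excluded here. A share of past users near zero is plausible, so any range should start at zero. This stands.

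Four stronger readings are tempting, and the documents do not support them.

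- *A reader might infer that prior use goes unrecorded.* The screening survey and the visit 1 checklist are not reproduced, so they may ask about it. What can be said is that the listed criteria would not exclude such a person.
- *A reader might infer that visitors to the manufacturer's webpage are largely its customers.* The only support is the market value in section 6, which covers active product and placebo together and is weak evidence of consumer sale.
- *A reader might infer that blinding is broken.* Recognition needs a perceptible difference between the arms. Section 15 (Potential Risks) lists gastrointestinal discomfort as possible with the supplement, but nothing says whether the placebo differs in this respect. If the contents do differ, the root problem is the matching of the placebo, which an eligibility question would only partly address.
- *A reader might infer that carry-over favours one arm.* Past users are randomised, so it falls on both arms in expectation. Stool before the antibiotic, and the other measures at visit 2, capture part of it at baseline. Persistence of these species beyond one month is not documented. The three-day antibiotic should not be counted as a washout, however: section 14 gives it to aid engraftment, and section 15 calls the microbiota changes from short courses minimal and reversible.

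The recognition argument is also confined to the self-reported scales. Body composition scans, blood measures and sequencing are far less open to expectation.

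**Conclusion.** The gap in eligibility is in the text: the trial is advertised on the manufacturer's webpage, and past users of its product who stopped more than a month earlier qualify. The consequences are conditional. Bias in self-reported anxiety, depression and cravings requires that past users enrol and that they can tell the arms apart; carry-over could dilute the rise in the product's species but would not favour an arm. On the assumptions shown, the bias lies between 0 and 0.18 SD. That is below one standard error (about 0.26 SD) throughout, and it may be negligible. Only near the upper end, with full recognition, does the type I error roughly double. This is a minor point, worth acting on because the remedy is cheap.

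**What to change.** Add to section 11 and to the screening survey an exclusion for any previous use of the trial product, or of another product of this manufacturer containing the same strains. Record the recruitment source for each participant.

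If past users are to be kept, record the use at visit 1 and repeat the self-report and stool comparisons without them as a pre-specified sensitivity analysis. Where participants have already been randomised, use this route; do not remove them from the main analysis.

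The cost is one screening question, one line in section 11 and one data field. The downside is a slightly smaller pool from one of several recruitment channels. No visit, sample or study treatment changes.
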